This study utilized an unblinded design. Parents were approached prior to surgery. After informed consent was obtained, infants were randomized to 1 of 2 arms: either the morphine PNCA with a basal infusion (PNCA) group, or the morphine COI group. Randomization was stratified by gender and surgical location (thoracic, upper or lower abdomen) in blocks of 4. The randomization scheme was created by a statistician on the research team using Windows version 6.0 of “rand.exe” (<http://block-stratified-randomization.software.informer.com/>). The clinical research coordinator used the scheme to assign participants to groups.

Protocol Details

Morphine was administered using PNCA for Group 1 and COI for Group 2. Conditions were designed to replicate current pain management procedures in our NICU. For the PNCA group, orders were entered by a member of the Acute Pain Service (APS) or the patient's anesthesiologist. Using a 250 mcg/mL solution, PNCAs were ordered as morphine 0.010-0.0125 mg/kg button dose, 8 min lockout, 0.010-0.0125 mg/kg/hr basal rate, and 0.060 mg/kg/hour total maximum. Doses were rounded to the nearest microgram. Parents were instructed on signs of pain, to only push the PNCA button when the child was awake and in pain, never to push the PNCA button when the child was asleep, and to notify their nurse if they felt their child's pain was not well controlled. For the COI group, morphine was ordered at 0.030 mg/kg/hr with a 0.030 mg/kg/hr nurse bolus available each hour to a maximum of 0.060 mg/kg/hr total. Parents were instructed on signs of pain and to notify their nurse if their child's pain was not well

controlled. The post-surgical opioid delivery system was initiated upon return to the NICU. Based on our current practice, PNCA patients were managed by the APS and COI patients were managed by the neonatology team. COI patients were checked on daily by the APS, but opioid adjustments were made only by the neonatology team. Monitoring of all patients was consistent with current practice. Patients had continuous pulse oximetry and cardiopulmonary monitoring. Pain and sedation scores (Hoffman, Nowakowski, Troshynski, Berens, & Weisman, 2002) were recorded at least every 2 hours for the first 24 hours, with a minimum of every 4 hours thereafter. To calculate total opioid consumption, PNCA doses (PNCA group) and morphine boluses (COI group) were documented hourly.

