Enrolled patients who at any point prior to PNCA or COI discontinuation, subsequently required vasopressors, a high frequency oscillating ventilator, or benzodiazepines, acetaminophen or anti-inflammatory agents as adjuncts for pain were discontinued early from the study. At the time of the study, acetaminophen was not used as routinely as it is now. In order to not confound pain assessment and opioid consumption by having some patients receive it and others not, the study team chose to stop data collection if acetaminophen (or benzodiazepine) was administered. Data collection terminated for all other patients when the PNCA or COI was discontinued. However, patient orders were monitored for 5 additional days to assess whether methadone was started.

Independent variables were collected to describe the sample and to determine whether groups were equivalent on all potentially confounding variables. Demographic and anthropometric data were extracted from the electronic health record, and included gender, race, ethnicity, gestational age, weight at time of surgery, total time PNCA or COI was used, and whether the current surgery was the infant's first. We also recorded mechanical ventilation and

any unplanned re-intubation occurrences. PNCA injections and attempts, as well as COI boluses were recorded for day (0700-1859) and nighttime (1900 – 0659) shifts. Mothers were asked about perinatal use of antidepressant or illicit drugs.

Primary Outcome

Our primary outcome was opioid consumption, defined as the average amount of opioid consumed over the time on study, and reported in mg/kg/hr. For the PNCA group, it was calculated based on the number of hourly injections plus the basal rate. For the COI group, it was based on the infusion rate across the time on study and any boluses administered.

Secondary Outcomes

- 1) Average pain intensity over the time on study. Participant pain intensity was assessed using the Revised-Face, Legs, Activity, Cry, Consolability (Revised-FLACC) scale (Malviya, Voepel-Lewis, Burke, Merkel, & Tait, 2006), the scale currently used in our NICU for this patient population. The FLACC has been used previously for NICU infants (Ahn, Kang, & Shin, 2005), has been validated in numerous pediatric populations (McGrath et al., 2008), and was originally validated in children from 2 months – 7 years (Merkel, Voepel-Lewis, Shayevitz, & Malviya, 1997).

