Statistical analyses were calculated using SPSS 24 (IBM SPSS Inc., Chicago, IL) and SAS 9.4 software (SAS Institute Inc.). An unadjusted two-sided $P < .05$ was used for statistical

significance in all analyses. Unless otherwise noted, all analyses include data from post-operative days (POD) 0-3. All participants who received the allocated intervention, and had at least one post-randomized outcome were included in the modified intent-to-treat analyses. In addition, descriptive and frequency analyses were used to provide summary information about patient characteristics. We report the median (Mdn) with Interquartile range (IQR) throughout. A Wilcoxon signed rank test was used to compare paired data of day and nighttime injections and attempts for the PNCA group, and paired day and nighttime boluses for the COI group. A Mann Whitney test was used to compare PCNA and COI groups; comparisons based on categorical data were analyzed using Chi-square or Fischer's exact tests. We used a mixed model with random post-operative day (POD) to examine the associations between opioid consumption and considered covariates, which included race, gender, surgery location, gestational age, study group and POD. Covariance structure used was AR(1), model was estimated by using maximum likelihood, POD and intercept were modelled as random effects. To meet the normality assumption of the linear mixed model, the outcome opioid consumption was transformed by using logarithm at base 10. For model selection procedure, we first included one of the considered covariates in the model to examine any time-varying effects on the outcome (univariable model analysis), then repeated the same procedure for other covariates. Based on the univariable model analyses, any covariates and interaction terms with $P < 0.20$ were included in the final multivariable analysis. The final model only includes those covariates with $P < 0.05$. Adverse events are reported based on incidence collapsed across POD.

Sample Size/Power Analysis

Based on our retrospective study (Czarnecki et al., 2014), and using an estimate of a large effect size, we planned to include 30 patients in each group (60 patients total). This sample size

would have allowed for an 80% power at 5% significance level to use a t-test to detect opioid consumption differences between groups of at least 0.74 SD. The study was terminated early however, due to difficulty recruiting, time and cost constraints.

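### The day/night comparison of PNCA injections, attempts and COI boluses states no hourly denominator, so unequal hours on the device can produce a false day/night difference

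*Combined protocol and SAP*

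**What the plan says.** Under Protocol Details, the shift data are defined: "PNCA injections and attempts, as well as COI boluses were recorded for day (0700-1859) and nighttime (1900 – 0659) shifts". Under Statistical Analysis and Data Management, "A Wilcoxon signed rank test was used to compare paired data of day and nighttime injections and attempts for the PNCA group", together with "paired day and nighttime boluses for the COI group". Neither place gives the unit of analysis (count or rate), the level at which values are paired (infant, post-operative day or shift), or how a partly observed shift is treated.

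The hours at risk are set elsewhere:

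- Start: "The post-surgical opioid delivery system was initiated upon return to the NICU" (Protocol Details).
- Usual end: "Data collection terminated for all other patients when the PNCA or COI was discontinued".
- Early end: "the study team chose to stop data collection if acetaminophen (or benzodiazepine) was administered". Other events listed in the same paragraph also end participation early.
- Analysis window: "Unless otherwise noted, all analyses include data from post-operative days (POD) 0-3". This includes the partial day of surgery. The clock boundary of a post-operative day is not defined.

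By contrast, the Primary Outcome section defines opioid consumption in mg/kg/hr. Protocol Details also says that PNCA doses and COI boluses were logged every hour, and that total time on the device was collected.

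**The concern.** The two shifts have the same nominal length of 12 hours, but they supply equal hours at risk only if the device runs through both. Pairing removes differences between infants in how much they use the device. It does not remove a difference between day and night hours within the same infant. If that difference leans the same way in most infants, a signed-rank test on counts will detect it as though it were a difference in use.

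What is at stake is the interpretation of a within-arm contrast. A reported day/night difference in button use or boluses could reflect only hours observed.

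**Working it through.** **The plan's own figures.** The documents give no figure for this comparison. The planned 30 infants per group is used below as one sample size. It reproduces for the primary outcome: a two-sided 5% t-test with 30 per group has 80.5% power at 0.74 SD.

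**Hours on the device.** Let the device start at clock time s on POD 0 and stop at clock time e on POD k, both within 07:00-19:00.

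- Day hours D = (19 − s) + 12(k − 1) + (e − 7)
- Night hours N = 12k
- Hence D − N = e − s

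The imbalance is the gap between the stop and start clock times. It is zero when they match, favours night when the stop is earlier in the day than the start, and favours day when it is later. At a constant hourly rate the ratio of expected night to day counts is N/D. All clock times below are assumptions.

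| Start | End | D (h) | N (h) | N/D |
|---|---|---|---|---|
| 14:00 | 10:00 POD 1 | 5 + 0 + 3 = 8 | 12 | 1.50 |
| 14:00 | 10:00 POD 2 | 5 + 12 + 3 = 20 | 24 | 1.20 |
| 16:00 | 10:00 POD 2 | 3 + 12 + 3 = 18 | 24 | 1.33 |
| 15:00 | 07:00 POD 2 (40 h) | 4 + 12 + 0 = 16 | 24 | 1.50 |
| 14:00 | 14:00 POD 2 | 5 + 12 + 7 = 24 | 24 | 1.00 |
| 12:00 | 18:00 POD 2 | 7 + 12 + 11 = 30 | 24 | 0.80 |

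The undefined POD boundary matters too. For a 14:00 start and a device still running at the end of the window, a cut at midnight ending POD 3 gives 41 v 41 h. A cut at the end of the following night shift gives 41 v 48 h (N/D = 1.17).

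**Simulation 1.** There is one pair per infant, with Poisson counts at the same hourly rate day and night. Between-infant rates are gamma with CV 0.7. Stops fall on POD 1, 2 or 3 with equal chance, except in the row with a fixed end. The signed-rank test is two-sided at 0.05, with 1,500 trials per setting. Rejection on raw counts at 0.5, 1 and 2 events per hour:

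| Start; stop | 12 infants | 30 infants | Direction |
|---|---|---|---|
| 12:00-17:00; 08:00-12:00 | 33%, 51%, 75% | 69%, 91%, 99% | night |
| 12:00-17:00; end of night shift after POD 3 | 37%, 65%, 86% | 80%, 98%, >99% | night |
| 12:00-17:00; 12:00-17:00 | about 5% throughout | 4-5% | none |
| 10:00-13:00; 15:00-19:00 | 39%, 60%, 84% | 76%, 95%, >99% | day |

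The same test on counts divided by hours on the device rejects in 4.5% to 7.0% of trials across all settings. Two events per hour is relevant to PNCA only. For COI the stated hourly maximum leaves room for (0.060 − 0.030)/0.030 = 1 bolus per hour.

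**Simulation 2.** Starts are at 12:00-19:00 and stops on POD 2 or 3, with 0.25 to 1 event per hour.

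- Stops 07:00-12:00: 53-96% (30 infants), 26-72% (15 infants).
- Stops spread over 07:00-19:00: 13-28% (30 infants), 7-17% (15 infants).
- Rare events, 0.05 to 0.1 per hour, 15 infants: 12-13% with morning stops, 5-7% with spread stops.
- Hourly rates: about 5%.

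**Use that declines after surgery.** With an assumed half-life of 12 to 24 h, 0.5 events per hour and stops at 07:00-19:00, raw counts reject 26-54% of the time and hourly rates 10-18%. Dividing by hours removes most of the problem but not all of it.

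**The case against.** A reader might infer that raw counts were definitely analysed. The documents do not say so: they are silent on the unit, the primary outcome is per hour, and doses were logged hourly. The gap may therefore lie only in the description. That stands as a limit. The plain meaning of the tested variables is still counts per shift, and nothing in the text would lead a second analyst to divide by hours.

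A reader might also infer a false night excess in particular. The documents do not support a direction. They give no surgery, start or stop times, and the working shows a night excess, a day excess or no bias according to what is assumed. The 15:00 start with a 40-hour run is an extreme case: it ends at the clock time that maximises the night excess for that start, and continuing to 15:00 would give no bias.

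The highest false-positive rates likewise depend on clustered clock times, frequent events and, for most of them, the full 30 infants. Recruitment ended early and the document gives no achieved number. For rare COI boluses the effect may be negligible.

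Finally, the comparison is within arm. Shift counts sit among the variables used to describe the sample and check group equivalence, not among the listed outcomes, and the plan states no conclusion about parental presence or night-time analgesia that would rest on them. All of this lowers the importance of the point. It does not remove the defect on the count reading.

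**Conclusion.** The point holds as a minor one. As written, the day/night signed-rank test has no hourly denominator. With partial first and last shifts, it can declare a difference when hourly use is identical. The size cannot be fixed from the documents: under assumed daytime starts it ranges from about the nominal 5% to over 90%. These figures rest on assumed clock times, event rates, a between-infant CV of 0.7 and a Poisson model that ignores the COI hourly cap.

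Two stronger conclusions are not supported: that the reported day/night result is wrong, and that the trial's main comparison is affected. The first would need the unit actually analysed and the start and stop times. The second fails because opioid consumption is already averaged over time on study.

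**What to change.** State the unit and the pairing level. For each infant, compute one day rate and one night rate: injections, attempts or boluses divided by hours on the device within 0700-1859 and within 1900-0659. Apply the signed-rank test to those pairs. Define the POD boundary, and report the day and night hours contributed. If rates were already used, one sentence saying so settles the matter.

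The cost is small: derive device hours by shift from the hourly records and rerun a simple test. There are modest downsides. Rates from very short exposures are noisy, and an infant with no hours in one shift type contributes no pair. Declining use after surgery is only partly handled. A sensitivity analysis limited to complete 24-hour periods would help check this, but it discards data and drops infants observed for less than 24 hours. For attempts, it also needs records finer than shift totals.

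### The Mann-Whitney comparison of PNCA with COI ignores the stratification factors; if gender and surgical location predict opioid consumption, it is conservative and forgoes power

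*Combined protocol and SAP*

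**What the plan says.** Design: "Randomization was stratified by gender and surgical location (thoracic, upper or lower abdomen) in blocks of 4". Two genders by three locations make six strata.

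Statistical Analysis and Data Management describes two analyses that bear on the arms:

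- A two-group test: "A Mann Whitney test was used to compare PCNA and COI groups". No stratification or adjustment is mentioned.
- A mixed model of log10 opioid consumption with candidate covariates, "which included race, gender, surgery location, gestational age, study group and POD". Terms enter the multivariable model at a univariable P below 0.20. Then: "The final model only includes those covariates with" P below 0.05. Both stratification factors, and study group itself, fall under this rule.

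The significance level is set by "An unadjusted two-sided $P < .05$ was used for statistical" significance throughout.

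Sample Size/Power Analysis: "we planned to include 30 patients in each group (60 patients total"), giving "80% power at 5% significance level to use a t-test" to detect "opioid consumption differences between groups of at least 0.74 SD". The same section reports that the trial stopped early. The final number of infants is not given.

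No sentence says whether the Mann-Whitney test or the mixed model is the primary test of opioid consumption.

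**The concern.** Stratified blocks keep the arms nearly balanced on gender and location, so variation between strata largely cancels out of the difference between arms. An unstratified test still counts that variation as noise. If the factors are prognostic, its standard error is too large for the design, its P values are too large on average under the null, and its true type I error is below 5%.

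The plan therefore sets up balance by design, and no stated analysis is certain to use it. In a trial that stopped short of its target, precision that is available from data already recorded is worth having.

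**Working it through.** **Step 1: the plan's own figure.** Inputs from Sample Size/Power Analysis: 30 per arm, difference 0.74 SD, 5% level (two-sided, from the Statistical Analysis section), t-test.

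- Normal approximation: n per arm = 2(1.960 + 0.842)² / 0.74² = 28.7, so 29.
- Two-sample t-test: noncentrality 0.74 × √(30/2) = 2.87 on 58 degrees of freedom gives power 80.5%. The n for exactly 80% is 29.7, so 30. The smallest difference detectable with 80% power at 30 per arm is 0.736 SD.

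The stated figure reproduces.

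**Step 2: size by formula.** Let R² be the share of within-arm outcome variance explained by gender and location. The documents give no value, so it is an assumption and is varied. With perfect balance, the unadjusted statistic has standard deviation √(1 − R²) under the null instead of 1:

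- True level of an unadjusted mean comparison = 2[1 − Φ(1.960/√(1 − R²))]. For R² = 0.1, 0.2, 0.3 this is 3.9%, 2.8%, 1.9%.
- Adjusted test: standardised difference 0.74/√(1 − R²) on 60 − 2 − 3 = 55 degrees of freedom. Power is 80.4% at R² = 0, and 84.3%, 88.3%, 92.0% at 0.1, 0.2, 0.3.

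**Step 3: simulation of the design.** Six equally likely strata, permuted blocks of 4, normal outcome with total within-arm SD 1, R² split equally between the two factors, N = 60, 8,000 runs per cell. Simulation error is about √(0.8 × 0.2/8000) = 0.4 point on power and √(0.05 × 0.95/8000) = 0.2 point on type I error. Power is at 0.74 SD; all entries are percentages.

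| R² | Mann-Whitney type I | Mann-Whitney power | Unadjusted t-test power | Stratified rank (van Elteren) power | Linear model, both factors forced: type I | Linear model, both factors forced: power | Linear model, P-value selection: power |
|---|---|---|---|---|---|---|---|
| 0 | 5.0 | 77.9 | 80.1 | 74.5 | 5.1 | 79.8 | 80.3 |
| 0.1 | 3.5 | 78.9 | 81.7 | 78.7 | 4.8 | 84.4 | 84.0 |
| 0.2 | 3.2 | 79.9 | 82.5 | 83.3 | 5.1 | 88.0 | 87.7 |
| 0.3 | 2.2 | 80.8 | 83.9 | 88.0 | 5.1 | 91.9 | 91.7 |
| 0.4 | 1.4 | 82.7 | 85.4 | 92.0 | 5.0 | 95.3 | 95.3 |

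**Step 4: splitting the gap.** At R² = 0.2 the forced model leads Mann-Whitney by 88.0 − 79.9 = 8.1 points. Of this, 82.5 − 79.9 = 2.6 come from ranks on normal data and 88.0 − 82.5 = 5.5 from adjusting. The rank part is 2.2 points at R² = 0 and 2.6 to 3.1 at R² = 0.1 to 0.3.

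**Step 5: the selection rule.** The last column applies the P < 0.20 and P < 0.05 rule to gender and location in a single-outcome linear model with study group always kept. Power stays within 0.5 point of forcing both factors in, and type I error is 4.8% to 5.3%. A factor is dropped mainly when it explains little.

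**Step 6: a smaller trial.** N = 30 in total is illustrative only; 4,000 runs per cell. At R² = 0.2, power is 45.4% for Mann-Whitney, 57.1% with the factors forced and 56.3% under selection. At R² = 0.4 the figures are 43.9%, 70.7% and 69.0%. Selection therefore costs about 1 to 2 points.

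**The case against.** Four arguments count against pressing this further.

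*The size is unknown.* Every loss depends on how well gender and location predict consumption in mg/kg/hr, and the documents do not report that. At R² = 0 Mann-Whitney holds its 5.0% level, and a stratified rank test would have about 3 points less power. This stands: the point must be stated conditionally.

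*The mixed model may be the main analysis.* It is the only inferential method that names opioid consumption, and it considers both factors. A reader might infer that the primary comparison ignores the strata; the documents do not say which analysis is primary. A reader might also infer that dropping non-significant factors makes the model conservative or costs it much power; Step 5 shows otherwise. Both corrections stand. However, study group is itself only a candidate in that model, so the Mann-Whitney test is the one group comparison certain to be reported.

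*Planned power is kept.* A reader might infer that ignoring the strata drags power below 80%. At N = 60 it does not: Mann-Whitney power rises from 77.9% to 82.7% as R² goes from 0 to 0.4, and the shortfall at R² = 0 is the price of ranks. What is missed is a gain.

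*The alternative was tested only on normal outcomes with equal spread.* Protocol Details gives the arms different infusion and bolus rules, so equal spread is not assured. This stands as a condition on the fix. The check also says nothing about the average pain score.

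**Conclusion.** The point holds as one of efficiency. The Mann-Whitney comparison does not account for the factors used to stratify the randomisation. If these explain 10% to 30% of the variance, its type I error at N = 60 is about 3.5% to 2.2%, and it forgoes about 6 to 11 points of power at 0.74 SD, of which 2 to 3 are due to ranks. If they explain almost nothing, adjusting makes no material difference.

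The error is in the safe direction, so a significant Mann-Whitney result is not put in doubt by this. Keeping the factors in the mixed model is right because they are part of the design; the measured loss from selecting them by P value is small.

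Assumptions: R² as varied, equal strata, a normal outcome, and a single-outcome linear model standing in for the mixed model. Not simulated: repeated days, the other candidate covariates and interactions, and selection applied to study group itself.

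**What to change.** - Add a group comparison: a linear model of each infant's log10 average opioid consumption on study group, gender and surgical location (3 levels), all forced in. Report it beside the Mann-Whitney result. As data collection is finished, label it as a re-analysis.
- Check the residual spread by arm before relying on it, because the arms have different dosing rules.
- Keep study group, gender and surgical location in the mixed model by design, whatever their P values. Apply the selection rule only to the other candidates.
- State which analysis of opioid consumption is primary.

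Additive terms are preferable to a six-stratum rank test: the strata are small, averaging 60/6 = 10 infants even at full size, and the stratified rank test had about 4 to 6 points less power than the linear model for R² between 0.1 and 0.3.

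Cost: three degrees of freedom (one for gender, two for location), a few lines of code and revised wording. Both factors were used to randomise, so no new data are needed.

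### No analysis of opioid consumption is named primary, so study group can be tested at unadjusted P<.05 both by a Mann-Whitney test and by a mixed model in which group is a selectable covariate

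*Combined protocol and SAP*

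**What the plan says.** The Primary Outcome section defines one value per infant: "Our primary outcome was opioid consumption, defined as the average amount of opioid consumed over the time on study, and reported in mg/kg/hr".

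The Statistical Analysis and Data Management section then gives two ways to compare the arms.

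- A rank test: "A Mann Whitney test was used to compare PCNA and COI groups". The sentence does not say which outcomes it covers.
- A linear mixed model: "We used a mixed model with random post-operative day (POD) to examine the associations between opioid consumption and considered covariates". The candidate list is the one "which included race, gender, surgery location, gestational age, study group and POD", and "the outcome opioid consumption was transformed by using logarithm at base 10".

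The model is built by selection. The plan says that "we first included one of the considered covariates in the model to examine any time-varying effects on the outcome", and repeats this for each covariate. Covariates and interactions with P<0.20 go forward, and the final model keeps those with P<0.05. Study group is not exempted.

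One significance rule covers everything: "An unadjusted two-sided $P < .05$ was used for statistical" significance in all analyses.

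The Sample Size/Power Analysis section plans 30 infants per group for 80% power at 5% "to use a t-test to detect opioid consumption differences between groups of at least 0.74 SD". No t-test appears among the listed analyses, and no sentence says which analysis decides the primary comparison.

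**The concern.** With two group tests on the primary outcome, each at unadjusted .05 and neither given priority, a significant result from either could be reported as the trial's answer. The 5% level in the sample-size section describes one test, not that choice.

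The two routes also estimate different things. One is a rank comparison, presumably of infant averages. The other is an effect on repeated log10 values with covariates chosen by P value. They can disagree, and the plan does not say which prevails.

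The retention rule adds a reporting problem. Read literally, study group stays in the final model only if its P value is below 0.05, so the model's group estimate is shown only when it is significant. Such an estimate is biased away from zero, and a null result from this route would leave no estimate to report.

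**Working it through.** **1. The plan's own figure.** Inputs from Sample Size/Power Analysis: difference 0.74 SD, 80% power, 5% significance. Two-sided normal approximation: n per group = 2 × (1.960 + 0.842)² / 0.74² = 2 × 7.85 / 0.5476 = 28.7, so 29. The exact t-test solution is 29.7, so 30. At 30 per group, t-test power is 80.5% and the minimum detectable difference is 0.736 SD. A one-sided test would need 23. The stated figure is reproduced as a two-sided t-test.

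**2. Cost of the t-test mismatch.** Replacing the t-test by Mann-Whitney at 0.74 SD under normality lowers power from about 80% to about 78%. This is minor.

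**3. Reference points for the false-positive rate.** With k independent tests at .05, P(at least one) = 1 − 0.95^k:

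- k = 2: 1 − 0.9025 = 9.75%
- k = 3: 1 − 0.8574 = 14.3%

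Tests on the same infants are correlated, so valid tests should fall between 5% and about these values.

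**4. Simulation under no group effect.** The documents give no variances, so all of these are assumed: natural-log SDs of 0.1-0.5 (intercept), 0-0.3 (slope) and 0.3-0.4 (residual); AR(1) correlation 0.2-0.6; 12-30 infants per group; POD 0-3. There were 18 scenarios of 10,000 runs, using tests valid at their nominal level.

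| Counted as a positive group result | At least one P<.05 |
|---|---|
| One named test | 5% |
| Mann-Whitney or overall group effect on log consumption | 5.6-8.7% (6-7% in most scenarios) |
| Those two or a linear group-by-POD term | 10.2-12.2% |
| Those two or a 3-df group-by-POD term | 10.4-12.8% |

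The absolute statistics of the two group tests correlate between 0.37 and 0.93, which is why two tests add little. The interaction supplies most of the rest.

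A separate, smaller simulation (60 infants, 2-4 device days each, REML fits, three assumed variance sets, 700 runs each) gave 6.1-6.6% for the two group tests and 10.7-11.4% with the interaction. Its Monte Carlo standard error near 11% is √(0.11 × 0.89 / 700) = 1.2 points.

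**5. Maximum-likelihood fits.** The plan specifies maximum likelihood. Fits by that method with Wald z tests and assumed unequal follow-up, without the plan's AR(1) term, gave the following (1,200 runs per row, standard error at most about 1 point):

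| Infants per group | Mann-Whitney alone | Model group alone | Either | Either, or group-by-POD |
|---|---|---|---|---|
| 30 | 6.2% | 7.1% | 8.3% | 14.2% |
| 15 | 5.1% | 7.7% | 8.2% | 14.9% |

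Part of this excess comes from the Wald tests themselves, which run above 5% in small samples, and not from multiplicity.

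**6. What was not simulated.** None of these runs applies the P<0.20 screen or the P<0.05 retention rule, and the final sample size is not in the documents. The figures show the scale of the problem and do not estimate this trial's error rate.

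**The case against.** The best defence is that the text already separates the roles. The Mann-Whitney sentence is the one written to compare the arms, and it suits an outcome with one value per infant summarised by medians. The mixed model is introduced to examine associations, with study group fifth of six covariates. On that reading there is one between-arm test and an exploratory model, and only a label is missing. This is a plausible intention, and it keeps the point modest. It does not remove it, because the text never states the hierarchy, applies the same unadjusted rule to both analyses, and lets study group be selected into the model on its own P value.

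The defence is right that the Mann-Whitney sentence names no outcome. That it covers opioid consumption is an inference. If it does not, the only group test of the primary outcome is the data-selected model, which is no better.

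A reader might infer more than the documents support:

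- **That the false-positive rate is about 11%.** This does not follow from two group tests. It requires counting group-by-POD as success, and the plan never writes that term; it is inferred from the references to time-varying effects and interactions. An interaction tests change over time, whereas the primary outcome is a single average. The variances are also assumed.
- **That the model's group coefficient becomes the POD 0 effect.** This depends on an interaction being kept and on how POD is coded, and the plan does not give the coding.
- **That the t-test mismatch undermines the power claim.** The loss is about 2 points. Early termination is likely to matter more.

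**Conclusion.** The point stands as a gap in specification with a moderate effect on error control. The plan allows at least two unadjusted tests of study group on the primary outcome, names neither as primary, and makes reporting of the model's group effect depend on its significance.

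Against 5% for one named test, the chance of at least one false-positive group result is about 6-9% for the two group tests. It is about 10-13% if an inferred group-by-POD term is also treated as success, and up to about 15% if that is done with Wald tests from maximum-likelihood fits. These ranges rest on variances, correlations and follow-up patterns that are assumed, and on the inference that the Mann-Whitney test covers opioid consumption. Nothing in the documents shows that an analysis was in fact chosen by its result.

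**What to change.** Name one primary test and one group contrast on each infant's average consumption over time on study. One suitable choice is a linear model of log10 average consumption on group, adjusted for gender and surgical location. The Design section names these as the stratification factors, and the model stays close to the t-test used for sample size.

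Then:

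- Report the mixed model as supportive, with study group forced in whatever its P value, and give one group contrast averaged over POD 0-3.
- Label any group-by-POD term exploratory.
- Give all other P values as nominal, and reserve the claim of statistical significance for the primary test.

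Timing matters. The Setting section puts data collection between April 2013 and April 2015, and the analysis text is in the past tense. A choice made after data collection cannot restore error control. It should be disclosed as post hoc, with the group result from every analysis reported.

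The cost is a few sentences of wording and, if the example is adopted, one additional simple model. The sponsor gives up claiming success on whichever analysis is significant.
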